toxicity within their respective domain. Among the 9 GTI domains, bone mineral density is excluded if the GTI will be measured at intervals shorter than 1 year, because bone densitometry is not sufficiently reliable in measuring changes at shorter intervals. Therefore, in the context of the ARGX-113-1904 trial with a maximum duration of 30 weeks, the index is truncated by removing the “bone mineral density” domain. Development of the GTI beyond the original validation work has suggested 2 approaches to analysis. These approaches provide complementary information about the ability of an investigational agent to reduce GC toxicity and also optimize the granularity with which the GTI captures the GC toxicity. The CWS is designed to assess cumulative GC toxicity, regardless of whether the toxicity has lasting effects or is transient. New toxicities that occur are added, but toxicities that appear to resolve on follow-up are not removed. Thus, the CWS serves as a lasting record of GC toxicity observed, and can only increase or remain the same over time. In the case of the presence of some GC toxicity at baseline, the AIS can be used to establish that a new therapy is effective at diminishing any baseline GC toxicity over time. With the AIS, toxicities can be removed if improvement occurs and added if worsening occurs. If toxicities present at baseline or occurring during the trial resolve over the course of follow-up, then that improvement is reflected in a negative score for that item during the interval. Both the CWS and the AIS are calculated for each interval, and then the interval scores are summed.

- The complementary GTI Specific List (GTI-SL) captures well-known glucocorticoid-related side effects. It is not weighted, and provides additional information in the domains most affected by glucocorticoid use during an individual’s treatment course. It comprises 11 domains (including 9 shared in common with the C-GTI) and 23 items. In this study, the item “major decrease in bone mineral density” will be excluded as bone matter density will not be assessed, and 22 items will be used.

The GTI with its 2 components (C-GTI and GTI-SL) are located in Section [10.15](#) (Appendix 15).

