9.5.8. Other Secondary Endpoints

The time to event and cumulative prednisone dose endpoints that are part of the other secondary efficacy endpoints will be analyzed in the mITT population (PV+PF participants) in line with the methodologies outlined above for the key secondary efficacy endpoints.

The remaining binary endpoints will be analyzed in the mITT population using the same methodology as for the primary endpoint (stratified CMH test).

The magnitude of the effect of efgartigimod PH20 SC compared to placebo in the PF subpopulation will be evaluated using the posterior distribution of the treatment effect (difference between efgartigimod PH20 SC and placebo) obtained in a Bayesian analysis. This Bayesian analysis will incorporate historical data for the placebo in an informative maximum a posteriori probability estimate prior with robustness modifier.⁴⁵ Details of this analysis will be included in the SAP.

Analysis of the continuous endpoints GTI-CWS and GTI-AIS (as components of the C-GTI) at week 15 and the EoS/ED visit will be analyzed in the mITT using the ANOVA model to compare both treatment groups (see Section 9.5.7). The complementary GTI-SL will be analyzed descriptively. More details on additional analyses (eg, correlation between GTI-CWS and GTI-AIS and cumulative or average daily prednisone dose) will be specified in the SAP.

Summary statistics and/or summary plots will be presented for all other endpoints, including PK, PD, immunogenicity, QoL, and self-administration training. More details for the analysis of the endpoints will be described in the SAP.

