10.15. Appendix 15: Glucocorticoid Toxicity Index (GTI)

Table 11: Approach to Calculating the Baseline GTI 2.0 Score: Toxicities Assigned Weighted Scores From C-GTI to Establish a Baseline GTI Score

[figure not shown]

Table 12: Approach to Calculating the Changes in GTI 2.0 Score: Weighted Scores Assigned to Improvements or Worsenings in the C-GTI

[figure not shown]
[figure not shown]

Table 13: GTI 2.0 Specific List: 11 Domains (9 of Which Are Shared by the C-GTI) and 23 Unique Items

GTI Supporting Information: Definitions

Glucocorticoid-induced myopathy definitions:

- Glucocorticoid myopathy is defined as mild symmetrical weakness of the proximal muscles and/or neck flexors associated with steroid therapy and NOT due to any other apparent cause. Muscle enzymes are typically within normal limits.
- Minor/Mild and moderate severity myopathy are defined by a muscle strength of grade 4 on the standard Medical Research Council Rating scale.
 - A 4 means weaker than normal but greater than antigravity strength against resistance.
 - “Minor” or “Mild” is mild weakness (Grade 4) that does NOT functionally limit the patient.
 - “Moderate” is mild weakness (Grade 4) that does impose functional limitations on the patient enough to interfere with normal daily activities.
 - Note that a person may have muscle weakness consistent with glucocorticoid-induced myopathy that is detectable on physical examination but the person is not aware of it or have any corresponding functional limitation. This would be classified as minor or mild.
- Severe glucocorticoid-induced myopathy, defined as a weakness of grade 3 or less (no more than antigravity strength and unable to overcome any resistance or any degree weaker), is included in the Specific List. People who are severely weak may have difficulty rising from a chair without assistance or other major functional limitations but the formal categorization should be based on the degree of weakness on strength testing.

Severity of glucocorticoid toxicity to the skin:

- Manifestations to be considered:
 - Acneiform rash
 - Easy bruising
 - Hirsutism
 - Atrophy/striae
 - Erosions/tears/ulcerations

Table 14: Severity Categorization of Skin Manifestations by Grade

Minor/Mild	Moderate	Severe (Specific Domain)
Acneiform rash (Grades 1-2)	Acneiform rash (Grade 3)	Acneiform rash (Grade 4)
Easy bruising (Grade 1)	Easy bruising (Grade 2)	
Hirsutism (Grade 1)	Hirsutism (Grade 2)	

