4.1.2.2 KEY SECONDARY ENDPOINTS (ALPHA CONTROLLED)

The following key secondary endpoints, which will be tested in the mITT population in hierarchical order (see section 4.1.4), are defined as:

- 1) The proportion of PV+PF participants that have achieved CRmin within 30 weeks using the same stratified CMH as for the primary endpoint. As this first key secondary endpoint is similar to the primary endpoint, the same approach for handling the main ICEs (both composite strategy and treatment policy strategy), as suggested for the primary analysis, will be applied.
- 2) Normalised cumulative Prednisone dose (NCPD, mg/kg/day) over the whole planned treatment phase in PV participants, will be analyzed by an analysis of covariance (ANCOVA) model to compare both treatment groups. Only actual administrations of prednisone are considered (not as scheduled). The model will include treatment and the stratification variables will be considered as factors.

Main intercurrent events are handled using the hypothetical strategy, that is, as follows:

- Intercurrent medications (see section 3.4.2): stop calculating cumulative dose after ICE. In case 'immunosuppressants for at least 4 weeks in total' is the ICE, use end of the 4 weeks IC medication as stop for cumulative dose calculation. In case ‘tetracyclines for at least 2 weeks in total' is the ICE, use end of the 2 weeks IC medication as stop for cumulative dose calculation. In case ‘IV or IM corticosteroids ' is the ICE, use the first day of this IC medication as stop for cumulative dose calculation.
- Discontinuation of IMP before CRmin due to lack of efficacy: stop calculating cumulative dose after this ICE.

Details on the derivation of intercurrent events are provided in Appendix 9.1.

	Statistical Analysis Plan	
ARGX-113-1904	Final analysis	Final 2.0 of 22NOV2023

A non-parametric stratified Mann-Whitney test will be performed as sensitivity analysis.

A supplementary analysis for this secondary endpoint will use the ‘treatment policy strategy’ where the occurrence of the intercurrent event is considered irrelevant: NCPD is calculated regardless of whether or not the intercurrent event occurs.

3) Time to CR in PV participants, calculated as the difference between the first date CR was achieved and the first IMP administration date.

Time to CR (days) = date (first CR) - first IMP date + 1

Main intercurrent events are handled as follows (composite strategy):

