Summary statistics on NCPD, cumulative prednisone dose, number of days and proportion of days with prednisone equivalent dose ≤ 10 mg will be provided for PV participants and an ANCOVA model with factors for treatment and the stratification variables will be applied on NCPD over the whole treatment phase only. Least square (LS) means and standard error (SE) with 95% 2-sided CI for placebo and efgartigimod will be reported, along with the difference in LS means of IMP vs placebo (with SE), 95% 2-sided CI, and 2-sided p-value. A non-parametric stratified Mann-Whitney test will be performed as sensitivity for PV participants. The 2-sided p-value resulting from this hypothesis test will signify whether the null hypothesis that the distributions of the NCPD for both treatment arms are identical can be rejected. The test will be conducted at a significance level of $\alpha=0.05$. A supplementary analysis using the treatment policy strategy applying the same ANOVA model will be done.

The table with summary statistics on NCPD will be repeated by subgroups, for PF participants and overall.

Time to CR and Time to DC will be descriptively presented with median times, quantiles and number and percentage of participants censored and with event. In addition, Kaplan-Meier survival plots by treatment arm will be produced (as in-text figures only). Both treatment groups will be compared using the stratified Fleming-Harrington weighted logrank statistic FH (1,0). Also the Cox proportional hazard model will be used: the model will include treatment as fixed effects and stratification factors as covariates. The HR for efgartigimod vs. placebo will be provided, along with the associated 95% 2-sided Wald-type CI and 2-sided p-value. The table will be produced for PV participants and overall. The descriptive statistics will also be presented by subgroups.

Duration of CRmin and other 'time to event' parameters of the 'other secondary endpoints' in section 4.1.2.3 will be descriptively presented and treatment groups will be compared using the logrank statistic.

	Statistical Analysis Plan	
ARGX-113-1904	Final analysis	Final 2.0 of 22NOV2023

Frequency tabulations will be provided for the percentages of treatment failure and its different reasons. Failure rates will be compared using the same CMH-test as for the primary endpoint analysis.

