Proportion of participants achieving DC and CR and proportion of participants with flare will be tabulated and treatment groups will be compared using the same CMH-test as for the primary endpoint analysis.

Descriptive statistics for PDAI on absolute values, changes from baseline and percent changes from baseline will be calculated per timepoint. Results will be presented separately for observed data and LOCF imputed data. Changes from baseline on LOCF imputed data will be compared between treatment arms at each analysis visit using an ANCOVA model with factors for treatment, baseline value and the stratification variables. Least square (LS) means and standard error (SE) with 95% 2-sided CI for placebo and efgartigimod will be reported, along with the difference in LS means of IMP vs placebo (with SE), 95% 2-sided CI, and 2-sided p-value.

The number of flares will be descriptively presented and analyzed by the same ANCOVA model as for the NCPD analysis. Time to the first flare will be presented and analyzed in the same way as time to CR or time to DC, however using the logrank statistic.

Frequency tabulations will be provided for the percentages of participants within each outcome of QoL questionnaire items (ABQOL and EQ-5D-5L). Additionally cumulative percentages (starting with the best outcome result) will be calculated. Descriptive statistics will be provided for the total ABQOL score and for the EQ-5D-5L VAS score. Changes from baseline will be analyzed by means of a mixed model for repeated measurements (MMRM). The model will include treatment, visit and treatment by visit interaction terms as fixed effects, with baseline value, interaction of baseline value with visit, and stratification factors as covariates. Within-subject correlation will be modeled by assuming an unstructured covariance matrix (UN) for the error terms and Kenward-Roger degrees of freedom method will be used. Least square means and SE with 95% 2-sided CI for placebo and efgartigimod will be reported, along with the difference in LS means of IMP vs placebo (with SE), 95% 2-sided CI, and 2-sided p-value.

If the default Newton–Raphson algorithm used by SAS PROC MIXED fails to converge, the following will be tried to avoid lack of convergence while maintaining an unstructured variance:

- A. The Fisher scoring algorithm (via the SCORING = 5 option of the PROC MIXED statement) will be used to obtain the initial values of covariance parameters.

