- B. If the above fails, the no-diagonal factor analytic structure will be used which effectively performs the Cholesky decomposition via the TYPE=FA0(V) option of the REPEATED statement, where V is the total number of distinct visits in the response vector (counting only rows where all model components are non-missing).
- C. If all the above fails, the variance-and-correlations parameterization will be attempted using TYPE =UNR.

	Statistical Analysis Plan	
ARGX-113-1904	Final analysis	Final 2.0 of 22NOV2023

In the rare case where all the above fails, the following covariance structures will be tested for convergence (in order): toeph, arh(1), csh, toep, ar(1) and cs. However, if one of these simpler covariance structures is used, this needs to be implemented in combination with sandwich variance estimator (EMPIRICAL option).

Descriptive statistics will be provided for the C-GTI scores AIS and CWS; treatment groups will be compared using the same ANCOVA model and stratified Mann-Whitney test as for the NCPD analysis. C-GTI will be analysed on complete cases: i.e. participants with C-GTI at least at baseline and post-baseline. Participants where first post-baseline GTI improvements/worsening have not been obtained with respect to the baseline moment but with respect to a later moment (i.e. no GTI assessment at baseline visit) are excluded from analyses and are only listed.

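### The C-GTI AIS comparison omits the baseline GTI score and is less precise than data already collected would allow (AIS only; a precision point, not a bias)

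*SAP*

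**What the plan says.** SAP 4.1.3 says of AIS and CWS that "treatment groups will be compared using the same ANCOVA model and stratified Mann-Whitney test as for the NCPD analysis". The model it borrows is set out earlier in that section: "an ANCOVA model with factors for treatment and the stratification variables will be applied on NCPD over the whole treatment phase only". SAP 4.1.2.2 describes it the same way: "The model will include treatment and the stratification variables will be considered as factors". The SAP calls it an ANCOVA, but it has no continuous covariate. Protocol 9.5.8 calls the C-GTI model an ANOVA and gives no baseline term either. The code note in SAP 9.2.2 says the script must be adapted to each model in section 4.1 and gives the baseline value for PDAI as an example; C-GTI is not mentioned.

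Elsewhere in SAP 4.1.3, PDAI change is compared "using an ANCOVA model with factors for treatment, baseline value and the stratification variables". The repeated-measures model for ABQOL and EQ-5D VAS contains baseline and baseline-by-visit.

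GTI is assessed at baseline, W15 and EoS/ED (Protocol 1.3, Schedule of Activities). Protocol Appendix 15 names a baseline score, "Table 11: Approach to Calculating the Baseline GTI 2.0 Score", although the table's content is a figure not reproduced in the text available. SAP 4.1.3 restricts the C-GTI analysis to participants with a baseline and a post-baseline C-GTI.

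**The concern.** The health impact of glucocorticoid use is a stated secondary objective, and C-GTI is its endpoint. Protocol 8.3.9 says that "the AIS can be used to establish that a new therapy is effective at diminishing any baseline GC toxicity over time". A score meant to show existing toxicity receding should depend on how much toxicity there was at the start. Eligibility mixes treatment-naïve newly diagnosed participants with relapsing participants who may already be on prednisone, so starting toxicity should vary. The disease-status factor captures part of that variation; the rest stays in the error term. The result is a wider confidence interval for the AIS difference than the data require, and any chance imbalance in baseline toxicity within strata stays in the estimate.

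**Working it through.** **1. Anchor for N.** The documents state no power, SD, effect size or baseline correlation for C-GTI. The only design figure to reproduce is in Protocol 9.3: 183 PV participants at 2:1 (122/61), 34% vs 11%, two-sided 5%, 95% power. Pooled proportion = (61×0.11 + 122×0.34)/183 = 0.263. Null SE = √(0.263×0.737×(1/61 + 1/122)) = 0.0691. Alternative SE = √(0.11×0.89/61 + 0.34×0.66/122) = 0.0587. Power = Φ((0.23 − 1.96×0.0691)/0.0587) = 94.7%, which agrees. It serves here only to fix N.

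**2. Terms in the models (SAP 4.1.3).**

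| Endpoint | Baseline term |
|---|---|
| PDAI change | yes |
| ABQOL and EQ-5D VAS change | yes, with baseline-by-visit |
| NCPD | no |
| C-GTI AIS and CWS | no |

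**3. How baseline enters AIS (SAP 9.3.1).**
- Myopathy, skin and neuropsychiatric items score below zero only on leaving a mild or moderate/severe state. Myopathy weights add up (54 + 9 = 63), so a participant starting at none cannot finish below 0 in that domain overall.
- BMI that stays below 25 scores 0.
- Glucose and blood-pressure improvement needs a starting value at or above a threshold, or a medication decrease.
- LDL can improve from any start above 1.81 mmol/L.
- Infection only worsens.

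**4. Effect on precision.** Let ρ be the partial correlation of AIS with baseline GTI, given the strata. In SD units, SE(ρ) = √(1/122 + 1/61) × √(1 − ρ²) = 0.157 × √(1 − ρ²). Equivalent N = 183/(1 − ρ²). Detectable difference at 80% power = (1.960 + 0.842) × SE. Power for an assumed 0.4 SD effect = Φ(0.4/SE − 1.96).

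| ρ (assumed) | SE | Reduction | Equivalent N | Detectable (SD) | Power at 0.4 SD |
|---|---|---|---|---|---|
| 0 | 0.157 | – | 183 | 0.439 | 72% |
| 0.2 | 0.154 | 2% | 191 | 0.430 | 74% |
| 0.3 | 0.150 | 5% | 201 | 0.419 | 76% |
| 0.5 | 0.136 | 13% | 244 | 0.380 | 84% |
| 0.6 | 0.125 | 20% | 286 | 0.351 | 89% |

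For PV+PF (142/71) the SE is 0.145 at ρ = 0, 0.139 at 0.3 and 0.126 at 0.5. The percentage reduction does not depend on N, so missing assessments do not alter it.

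**5. A plausible range for ρ.** AIS was simulated with the SAP 9.3 weights for myopathy, skin and neuropsychiatric items. Assumed inputs were:
- half of participants newly diagnosed;
- baseline toxicity per item of 2/10%, 5/15% or 10/30% (newly diagnosed/relapsing), 30% of it moderate/severe;
- 10, 30 or 50% improving and 5 or 10% worsening.

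Within-stratum correlation of AIS with baseline ran from −0.15 to −0.60, giving SE ratios of 0.989 to 0.802 (1% to 20% smaller). A simulation with seven improvable domains (20–40% baseline toxicity in relapsing participants, 0.4 times that in newly diagnosed, 30–60% resolving) gave ratios of 0.852 to 0.957, or 4–15% smaller. One with infection scored gave 3–18%.

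For CWS the first simulation gave an SE ratio of 1.000 throughout. The one with infection gave a reduction between −0.3% and +0.7% in all 32 scenarios.

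**The case against.** The strongest reply is that this is an efficiency preference. The SAP follows Protocol 9.5.8, randomization keeps the unadjusted estimate unbiased, and C-GTI lies outside the alpha-controlled sequence. All of that stands, and it sets the weight of the point.

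Second, the comparison with PDAI, ABQOL and VAS is imperfect. Those are changes on a scale that has its own baseline value, whereas AIS is a sum of transition weights, so a baseline GTI score would be a separately derived variable. That also stands, but a covariate need not be the outcome's own baseline to reduce residual variance.

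Third, the disease-status factor may already absorb part of the effect, and the gain rests on assumed inputs. This stands too. The correlations in step 5 are within stratum, but their inputs are not from the documents.

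Fourth, Table 11 cannot be seen, so it cannot be checked whether the score is computable from the collected data as it stands. The derivation therefore has to be written down.

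A reader might go further and infer that a negative AIS is possible only in a domain with toxicity at baseline. The documents do not support that. Protocol 8.3.9 also credits resolution of toxicity arising during the trial, SAP 9.3.1 scores against the previous assessment, and LDL, blood pressure and medication decreases can score below zero without it. The link is partial. Nor do the documents give any basis for calling baseline GTI the strongest available predictor.

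**Conclusion.** The omission is confirmed and nothing elsewhere in the SAP repairs it. For AIS, adjusting for the baseline GTI score would probably shorten the confidence interval; the size is unknown, about 1–20% in SE under the assumptions shown. For CWS a reader might infer the same loss, but CWS sums only worsening (SAP 9.3.2.1). Baseline caps it only for graded items already moderate/severe, infection is scored afresh in each interval, and blood pressure, LDL, HbA1c and BMI can worsen from a normal start. The simulations show no gain, and none is claimed.

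It would also be wrong to read this as a bias or as a threat to the trial's main results. It concerns precision and chance imbalance on an other secondary endpoint without alpha control. It is a worthwhile improvement at almost no cost, not a defect in the confirmatory analysis.

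**What to change.** Before unblinding, amend SAP 4.1.3 so that the AIS ANCOVA at Week 14, Week 30 and Overall includes the baseline C-GTI score as a continuous covariate beside treatment and the stratification factors. Keep the stratified Mann-Whitney test as sensitivity. For CWS the covariate is optional, for consistency only.

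Add the derivation to SAP 9.3, which now defines change weights only: score per Protocol Table 11, bone mineral density domain excluded as in Protocol 8.3.9, with a rule for missing baseline laboratory or blood-pressure values. State also that Week 30 AIS is cumulative from baseline, as SAP 9.3.2.2 has it. SAP 4.1.2.3 describes the last 16 weeks, an interval that starts from Week 14 and for which the baseline link would be weaker.

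Cost: one derived variable and 1 df. The complete-case rule means no analysed participant should be lost, and no new assessment is foreseen, subject to confirming that Table 11 can be computed from what is collected. Protocol section 9 allows minor method changes to be documented in the SAP without an amendment; list it in SAP 6.1.

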4.1.4 Fixed-Sequence testing procedure

To control the type I error for the primary and secondary endpoints (alpha controlled), the primary efficacy endpoint will be tested at the 5% 2-sided alpha level and will act as gatekeeper for the testing of secondary endpoints. The primary endpoint and secondary endpoints will be tested in a strict hierarchical order as listed below to control the type I error (for definitions see section 4.1.2.1 and 4.1.2.2). If a certain endpoint turns out to be non-significant at the 5% significance level, subsequent endpoints will no longer be evaluated.

1. Primary endpoint: the proportion of PV participants who achieve CRmin within 30 weeks using composite strategy approach
2. Proportion of PV+PF participants that have achieved CRmin within 30 weeks using composite strategy approach
3. NCPD in PV participants using hypothetical strategy approach
4. Time to CR in PV participants using composite strategy approach
5. Time to DC in PV participants using composite strategy approach
6. NCPD in PV+PF participants using hypothetical strategy approach
7. Time to CR in PV+PF participants using composite strategy approach
8. Time to DC in PV+PF participants using composite strategy approach

The individual per-endpoint tables will only show unadjusted p-values. A fixed-sequence testing procedure table will be produced. This table will show both unadjusted p-values and p-values adjusted for multiplicity. For a given endpoint, the adjusted-for-multiplicity p-value is calculated as the maximum between its unadjusted p-value and the highest of all unadjusted p-values tested before.

	Statistical Analysis Plan	
ARGX-113-1904	Final analysis	Final 2.0 of 22NOV2023

